1.2 Intravesical BCG Immunotherapy for NMIBC

BCG for intravesical use is a live attenuated form of *Mycobacterium bovis* and has been approved by the Food and Drug Administration (FDA) of the United States for the treatment and prophylaxis of carcinoma in situ (CIS) of the urinary bladder, and for the prophylaxis of primary or recurrent stage Ta and/or T1 papillary tumors following transurethral resection (TUR) (<https://www.fda.gov/downloads/BiologicsBloodVaccines/Vaccines/ApprovedProducts/UCM163039.pdf>). Per the American Urological Association (AUA) bladder cancer guidelines it is the standard treatment for patients with high-risk NMIBC following a restaging transurethral resection of bladder tumor. Patients with NMIBC have high recurrence rate after intravesical BCG with or without chemotherapy. Standard definitions of post-BCG states may be used to guide clinical decision-making and clinical trial design [5].

BCG failure: Patients with either intermediate- or high-risk NMIBC who received induction intravesical BCG but failure to achieve tumor response. Up to 40% of patients with NMIBC will fail intravesical BCG therapy [6].

BCG unresponsive: Patients have persistent or recurrent high-grade Ta/Tis or T1 bladder cancer after completion of at least induction (≥ 5 doses) and one round of maintenance (or second induction; ≥ 2 doses) intravesical BCG; or tumor recurrent within six months after initial response. Up to 50% patients with NMIBC have tumor progression after the third cycle intravesical BCG therapy [7].

The difficulty with management of NMIBC has resulted in many attempts to improve treatment. For patients with Ta disease, without additional treatment, cancer recurrence occurs in more than 60% and disease progression occurs in more than 20%. Patients with T1 disease may experience recurrence in more than 75% of patients with progression in 35% of patients. Intravesical chemotherapy may delay recurrence, but does not prevent progression. BCG has been shown to reduce disease progression and recurrence while improving survival. The most benefit from BCG is obtained with a complete maintenance course. Response rates can improve from nearly 40% to over 70% [8, 9]. However, very few patients can tolerate a complete full course of maintenance BCG (~16%) [9]. Patients with persistent tumor or post-BCG recurrence may respond to another challenge with intravesical BCG [10]. However,

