- m. For the subset of patients with CIS (with or without concomitant Ta or T1 disease) at study entry, a 6-month biopsy is required. A negative biopsy at 6 months will provide evidence of complete response. A +/- 10 day window will be allowed around the disease assessment time point. Patients receiving a second induction will not be required to undergo 6-month biopsy.
- n. Following avelumab infusions, patients must be observed for 30 minutes post infusion for potential infusion related reactions.

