8.2 Efficacy Evaluation

Cystoscopy and urine cytology will be obtained at screening and at Month 3, 6, 9, and 12. Only frankly malignant cytology will be considered positive and used to determine the need for bladder biopsy and further evaluation. Three-month complete response (CR) rate, 6-month CR rate, recurrence free survival (RFS), cystectomy-free survival (C

FS), and overall survival will be evaluated as the following.

Time to High-Grade Recurrence (TTHGR) is defined as time from date of first treatment to first high-grade recurrence. Patients without a recurrence will be censored at their last cystoscopy date. Those who die without a recurrence are also counted as a recurrence and high-grade recurrence at time of death.

Time to Recurrence (TTR) is identical to TTHGR with the addition that failure with any-grade bladder cancer is considered an event.

Progression-free survival (PFS) is defined as time from date of first treatment to first evidence of muscle invasive bladder cancer, metastatic disease, or death due to any cause. Those without an event are censored at their last valid tumor assessment, or at the last tumor assessment before patient start of the new therapy if a patient has started new anti-cancer therapy.

Complete Response: For the subset of patients with CIS (with or without concomitant Ta or T1 disease) at study entry, a 6-month biopsy is required. A negative biopsy at 6 months will provide evidence of complete response. A +/- 10 day window will be allowed around the disease assessment time point. Patients receiving a second induction will not be required to undergo 6-month biopsy

Duration of Complete Response: For the subset of patients with CIS (with or without concomitant Ta or T1 disease) at study entry who achieve a CR, duration is defined as time from first documentation of CR to time of first high grade recurrence. Patients who remain CR at end of study (EOS) are censored at their last cystoscopy date.

Overall survival (OS) is defined as the duration from the first dose date of the study drug until death due to any cause. Patients who are still alive at EOS are censored on the date they will be last known to be alive. An exploratory analysis to determine OS at EOS will be estimated by the Kaplan-Meier method.

Patient Reported Outcomes:

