2. Endpoints

a. Primary Endpoint

- i. Completion of induction therapy with combined BCG + avelumab as defined as freedom from dose-limiting toxicity (DLT) (Section 5.2.1) preventing completion of at least 5 of 6 treatments of BCG + avelumab within 8 weeks.

b. Secondary Endpoint

- i. 6 Month maintenance treatment completion as defined as completion of at least 2 of 3 maintenance treatments within a 5 week period without DLT or disease progression. Disease status will be evaluated based on cystoscopy and urine cytology prior to maintenance therapy. Patients with persistent or recurrent high-grade disease at 6 Month cystoscopy will be taken off treatment. Low-grade recurrence will be tolerated without treatment interruption.
- ii. 3-month and 6-month complete response (CR) based on negative cystoscopy and urine cytology.
- iii. Recurrence free survival (RFS) at 6 and 12 months, defined as proportion of patients who are alive and free of persistent or recurrent NMIBC based on cystoscopy, cytology and/or biopsy.
- iv. Progression-free survival (PFS) at 6 and 12 months, as defined by time from day of first treatment to first progression to higher grade or stage, including muscle-invasive disease or death from any cause
- v. Cystectomy-free survival (CFS), defined as time from study initiation to cystectomy or death
- vi. Overall survival, defined as time from day of first treatment to death from any cause

c. Exploratory Endpoint

- i. To obtain preliminary data of potential biomarkers that would associate with tumor response from the combination of avelumab and intravesical BCG.
- ii. Avelumab combined with intravesical BCG will improve quality of life in patients with NMIBC.

3. Design information

a. General statistical considerations

- i. This is a single arm, phase Ib study. A total of 18 evaluable patients will be enrolled at the Stephenson Cancer Center. More than 40 patients with bladder cancer initiate intravesical BCG treatment in our Urologic Oncology clinic each year, including approximately 40% patients with BCG-treated but unresponsive NMIBC (persistent or recurrent) who are hopefully eligible for the proposed study. Based on our prior experience with a similar patient population, we anticipate enrollment of 1 patient per month.

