- xxvii. Administration of a live/attenuated vaccine within 4 weeks prior to the first dose of study treatment, within 5 months following the administration of the last dose of study drug, or anticipation that such a live/attenuated vaccine will be required during the study.
- xxviii. Other severe acute or chronic medical conditions including immune colitis, inflammatory bowel disease, immune pneumonitis, pulmonary fibrosis or psychiatric conditions including recent (within the past year) or active suicidal ideation or behavior; or laboratory abnormalities that may increase the risk associated with study participation or study treatment administration or may interfere with the interpretation of study results and, in the judgment of the investigator, would make the patient inappropriate for entry into this study.

5. Analysis Populations

The analysis populations are defined as below.

- a. **Safety population:** All patients who receive at least one dose of combination avelumab and BCG will be included in the analyses of compliance and safety.
- b. **Biomarker population:** For biomarker analysis, the biomarker population will comprise all evaluable patients who have sufficient baseline and on-study biomarker measurements.
- c. **Evaluable population:** Evaluable patients will be defined as patients who receive at least 5 doses of intravesical BCG and avelumab IV weekly during induction treatment and complete the first post-treatment cystoscopy and/or urine cytology for tumor assessment. Patients

who discontinued study treatment due to toxicity incurred by previous therapy will be evaluated for safety analysis, but will be replaced by additional patients for the efficacy analysis.

Patients removed from study for early withdrawal or hypersensitivity reactions will be replaced if they have received less than 5 doses of study treatment during induction treatment, but will be included in the safety analysis.

Patients who do not receive at least 5 doses of intravesical BCG and avelumab IV during induction treatment will be considered unevaluable for efficacy analysis and will be replaced unless the missed doses were due to development of grade 3-4 adverse events related to study treatment.

Evaluable population will be used for the analysis of EORTC QOQ-C30 (Section 6) and antitumor measures (Section 8).

6. Patient Population Summary

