5. The following may be considered as exceptions to DLTs: 1.
- a. Grade 3 nausea, vomiting, or diarrhea and Grade 4 vomiting or diarrhea in the absence of maximal medical therapy that resolves in 72 hours.
 - b. Grade 3 fatigue lasting < 5 days.
 - c. Grade 3 hypertension that can be controlled with medical therapy.
 - d. An increase of indirect (unconjugated) bilirubin indicative of Gilbert's syndrome.
 - e. Serum lipase and/or serum amylase CTCAE Grade 3 ≤ 7 consecutive days without clinical signs or symptoms of pancreatitis.

ii. **Definition of DLT Evaluable Population**

1. Patients enrolled in safety lead-in cohort who receive at least 4 doses and complete the DLT observation period (the first 42 days of induction treatment), unless the patient discontinued the study treatment due to a DLT.

8. Antitumor Evaluation

- a. The proportion of patients receiving a complete induction course (at least 5 of 6 treatments of BCG + avelumab within eight weeks of starting treatment) at 3 months and at 6 months will be calculated and a 95% Wilson score confidence interval constructed for the completion rate.
- b. The 3-month and/or 6-month complete response (CR) rates will be summarized as the proportion (and 95% CI) of patients with complete tumor response at month 3 or 6 of study treatment. Patients who remain CR at end of study (EOS) are censored at their last cystoscopy date.
- c. The duration of response will be calculated as time from the date of first response (complete response (CR), partial response (PR), pathological complete response (pCR)) to the first date of non-response. Duration of response will be summarized using the Kaplan-Meier method. Median duration of response with 95% CI will be computed. Results will be presented in tabular and graphic form, as appropriate.
- d. Progression-Free Survival (PFS) at six month and twelve months is defined as the time in months from the first dose of the drug to the date of death or the first documented date of progression, whichever comes first. For patients who did not die and did not have progression, the PFS is censored at the last documented tumor assessment. Survival curve for PFS will be generated using the Kaplan-Meier method. Median PFS with 95% CI will be computed. Those without an event are censored at their last valid tumor assessment, or at the last tumor assessment before patient start of the new therapy if a patient has started new anti-cancer therapy.

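### The SAP's 6-month complete response rule omits the biopsy that Protocol 8.2 requires in patients with CIS at entry, so a biopsy-positive CIS patient can be counted as a responder

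*SAP*

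**What the plan says.** The CR endpoint appears in two forms.

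- SAP 2.b.ii, and Protocol 2.2.2 in the same words: "3-month and 6-month complete response (CR) based on negative cystoscopy and urine cytology". Neither names a biopsy or a disease subset.
- Protocol 8.2, under Complete Response, repeated in footnote m to Table 7: "For the subset of patients with CIS (with or without concomitant Ta or T1 disease) at study entry, a 6-month biopsy is required". It continues: "A negative biopsy at 6 months will provide evidence of complete response". An exemption follows: "Patients receiving a second induction will not be required to undergo 6-month biopsy".

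For the analysis, SAP 8.b reports the proportion "of patients with complete tumor response at month 3 or 6 of study treatment" with a 95% CI whose method is not named. SAP 5.c assigns the antitumor measures to the whole evaluable population. The SAP does not mention CIS. It does name biopsy as a basis for recurrence-free survival (RFS) in 2.b.iii and 8.f. No section says which CR rule governs the reported rate.

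**The concern.** Eligibility covers any NMIBC that is BCG-treated but unresponsive, so patients with CIS and patients with papillary disease only can both enter. For the CIS patients the trial obtains a biopsy at 6 months. The endpoint that the biopsy is meant to support is then defined without it.

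Two analysts, one working from SAP 2.b.ii and one from Protocol 8.2, could classify the same patient in opposite ways. The SAP could also contradict itself: one patient might be a CR under 2.b.ii and, on the same biopsy, not free of disease under 2.b.iii. Protocol 8.2 treats only frankly malignant cytology as positive, which leaves room for a negative cytology alongside a positive biopsy. With about 18 patients, one or two reclassifications visibly change the rate.

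**Working it through.** **1. The plan's own precision figure.** Protocol 10.1 and SAP 3.b.ii give a Wilson 95% lower bound of 37.6% for the Month 6 completion rate at n = 18 and p = 0.60. With z = 1.96 (z² = 3.84):

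- centre = (p + z²/2n) / (1 + z²/n) = (0.600 + 0.107) / 1.213 = 0.582
- half-width = z·√[p(1−p)/n + z²/4n²] / (1 + z²/n) = 1.96·√(0.01333 + 0.00296) / 1.213 = 0.206
- interval = 37.6% to 78.9%

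The stated bound reproduces. It belongs to the completion endpoint. The documents state no CR rate, CR target, CIS share or biopsy-positive rate. I use the same interval below to illustrate CR.

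**2. The two rules side by side at 6 months.** Each patient below has clear cystoscopy and negative cytology.

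| Patient | SAP 2.b.ii, Protocol 2.2.2 | Protocol 8.2, footnote m |
|---|---|---|
| CIS at entry, biopsy negative | CR | CR |
| CIS at entry, biopsy positive | CR | not CR (by implication) |
| CIS at entry, re-induced, no biopsy | CR | no rule stated |
| Papillary only | CR | not addressed |

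The second row is the conflict. The third is a gap: after the exemption, Protocol 8.2 gives no CR rule. At 3 months no biopsy is required anywhere, so the biopsy rule cannot change that rate.

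**3. Effect on an all-patient rate.** Each biopsy-positive CIS patient counted as CR adds 1/18 = 5.6 points. Assume, for illustration, 18 evaluable patients of whom 11 are negative on cystoscopy and cytology:

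| Biopsy-positive CIS among the 11 | 6-month CR | Wilson 95% CI |
|---|---|---|
| 0, or biopsy ignored | 11/18 = 61.1% | 38.6% to 79.7% |
| 1 | 10/18 = 55.6% | 33.7% to 75.4% |
| 2 | 9/18 = 50.0% | 29.0% to 71.0% |
| 3 | 8/18 = 44.4% | 24.6% to 66.3% |

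**4. Effect within the CIS subset.** The same patient weighs more here: 1/6 = 16.7, 1/9 = 11.1 or 1/12 = 8.3 points if 6, 9 or 12 of the 18 have CIS (assumed). Suppose 6 have CIS and 4 of them are negative on cystoscopy and cytology:

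- none of the 4 biopsy-positive: 4/6 = 66.7% (30.0% to 90.3%)
- one: 3/6 = 50.0% (18.8% to 81.2%)
- two: 2/6 = 33.3% (9.7% to 70.0%)

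**5. A sign of how the gap arose.** SAP 8.b adds that patients still in CR at end of study are censored at the last cystoscopy. In Protocol 8.2 that sentence belongs to duration of CR and applies to the CIS subset only. In the SAP it is attached to a proportion, which has no censoring, and the CIS qualifier is gone. This suggests that the restriction was lost in transfer, but does not prove it.

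**The case against.** The best defence is that the passages are complementary. Protocol 8.2 opens with cystoscopy and cytology at Months 3, 6, 9 and 12 for everyone and then adds a biopsy for CIS. It gives no 3-month rule, so it cannot be the whole CR definition. Read together, the passages give cystoscopy and cytology for all, plus the biopsy at 6 months for CIS. That is a fair reading of the Protocol, but the SAP contains only the first half and an analyst following it would not use the biopsy.

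Several stronger conclusions are tempting and are not supported:

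- **That the SAP departs from the Protocol.** Protocol 2.2.2 has the same wording as the SAP, so the inconsistency is also inside the Protocol.
- **That papillary-only patients are wrongly counted as responders.** Protocol 8.2 limits duration of CR to CIS, which hints at a CIS-only endpoint, but it never bars CR in papillary-only patients. The remark on BCG after resection in Protocol 1.2 describes approved use. No eligibility criterion requires resection before entry, so it cannot be said that these patients have nothing left to respond.
- **That the pooled rate is biased upward by a calculable amount.** A pooled rate that differs from the CIS rate describes a different population. Any figure for the gap would come from assumed CIS and papillary rates that the documents do not supply. Only the miscounted biopsy-positive patients are misclassified.
- **That the rate will mislead against the response of around 20% to repeat induction in Protocol 1.2.** No such comparison is planned, and that figure is not stated to be for CIS.

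It also stands that Month 6 completion, not CR, is called the most important secondary objective. The exemption for re-induced patients is a deliberate protocol rule; only their CR classification is missing.

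**Conclusion.** The concern holds for the 6-month CR rate in patients with CIS at entry. As written, SAP 2.b.ii and 8.b count a CIS patient with a positive 6-month biopsy as a complete responder when cystoscopy and cytology are negative, contrary to Protocol 8.2 and footnote m, and possibly contrary to the SAP's own RFS rule. The error can only raise the 6-month rate, by 5.6 points per patient at n = 18. How many patients would be affected is unknown and may be none.

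The denominator of 18 is the planned evaluable number. Protocol 10.2 instead points to the Section 8.1.1 population (at least one dose of each agent), which would make the denominator larger and the step smaller if more patients were treated.

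This should be fixed before CR is tabulated. It does not threaten the trial's decisions, because CR carries no test, threshold or stopping rule.

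**What to change.** Align SAP 2.b.ii and 8.b with Protocol 2.2.2 and 8.2 on one text:

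1. For patients with CIS at entry, 6-month CR needs clear cystoscopy, negative cytology and a negative biopsy. A positive biopsy is a non-CR.
2. Report the 3- and 6-month CR rates by CIS status at entry, with CIS and papillary-only on separate lines, each with its denominator and a Wilson 95% CI. Label any all-patient rate as such.
3. Keep re-induced CIS patients who are exempt from the biopsy in the CIS denominator, show them on a separate line and do not count them as biopsy-confirmed CR.

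Restricting CR to CIS altogether is a choice of target population open to the sponsor, and is not needed to remove the conflict.

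The cost is wording in both documents and one more table split. No new biopsy or visit is needed. The subset intervals will be wide: about 60 points for 4/6 against about 41 points for 11/18. The reported 6-month rate may be lower.

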2.1.4 Exploratory Objective

- To identify potential biomarkers that would associate with tumor response from the combination of avelumab and intravesical BCG.

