2.2.2 Secondary Endpoints

- 6 Month maintenance treatment completion as defined as completion of at least 2 of 3 maintenance treatments within a 5-week period without unacceptable toxicities or disease progression. Disease status will be evaluated based on cystoscopy and urine cytology prior to maintenance therapy.

Patients with persistent or recurrent high-grade disease at 6 Month cystoscopy will be taken off treatment. Low-grade recurrence will be tolerated without treatment interruption.

- 3-month and 6-month complete response (CR) based on negative cystoscopy and urine cytology.
- Recurrence free survival (RFS) at 6 and 12 months, defined as proportion of patients who are alive and free of persistent or recurrent NMIBC based on cystoscopy, cytology and/or biopsy.
- Progression-free survival (PFS) at 6 and 12 months, as defined by time from day of first treatment to first progression to higher grade or stage, including muscle-invasive disease or death from any cause
- Cystectomy-free survival (CFS), defined as time from study initiation to cystectomy or death
- Overall survival, defined as time from day of first treatment to death from any cause

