- b. If history, PE, ECOG-PS and screening laboratory tests are performed within 72 hours prior to first dose (Cycle 1, Day 1), repeat testing is not required.
- c. Tumor assessment via CT or MRI will be optional at screening if data from standard care is available.
- d. **Toxicity assessment is required prior to each BCG and/or avelumab treatment.** If dose interruption or modification is required at any point on study because of hematologic toxicity, weekly CBC will be monitored until the AE resolves, and to ensure safety of the new dose, weekly blood draws for CBC will be also required for an additional 4 weeks after the AE has been resolved to the specified levels, after which monitoring every 3 weeks may resume.
- e. Consisting of albumin, alkaline phosphatase, BUN, calcium, carbon dioxide (CO₂), chloride, creatinine, glucose, potassium, AST, ALT, sodium, total bilirubin, total protein
- f. Patients will undergo EKG monitoring at screening. Additional EKG at pre-dose on day 1 of each cycle and EOT if clinical indicated.
- g. Blood sample for exploratory biomarkers will be collected at pre-dose on day 1 of induction therapy; and at pre-dose on day 1 of month 3 and month 6 maintenance therapy.
- h. Urine sample will be collected at pre-dose on days 1, 22 and 43 of induction treatment; and at pre-dose on day 1 of Months 3 and 6 Maintenance for measurement by multiplexed immunoassay for immune response biomarkers.
- i. Cystoscopy and urine cytology will be obtained at screening and at Month 3, 6, 9, and 12 and at EOT. Only frankly malignant cytology will be considered positive and used to determine the need for bladder biopsy and further evaluation.
- j. Patient will be asked to complete EORTC QLQ-C30 to measure QOL on BCG [33].
- k. Every three months for up to one year. See Sections 7.2.1 and 7.2.2 for additional details.
- l. During the COVID-19 crisis, protocol mandated visits may be performed via telemedicine or visits may be combined in order to prevent imminent safety risks to patients. All such changes to the visit schedule must be clearly documented in the subject's chart. Changes in study visit schedules or missed visits must be explained in the final clinical study report.

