7.3 Biological Sample Collection for Translational Study

We will assess immune profile in the pre- and post- treatment urine and blood as potential biomarkers that would associate with tumor response from the combination of avelumab and intravesical BCG. The analysis of other molecular profile may be optional if sample of cystoscopy and urine cytology is available.

7.3.1 Urine collection:

Urine will be collected before BCG treatment on the following days:

BCG Induction phase:

- Week 1 day 1 (Day 1, before BCG treatment)
- Week 4 day 1 (day 22, before BCG treatment)
- Week 7 day 1 (day 43)

BCG maintenance phase:

- Day 1 of Month 3 and 6 Maintenance: before BCG treatment

Urine specimen will be sent to the Stephenson Cancer Center biorepository for storage, which will be analyzed using a multiplexed immunoassay if collaborative funding is available.

7.3.2 Blood collection:

Blood sample for exploratory biomarkers will be collected before BCG treatment on the following days:

BCG Induction phase:

- Week 1 day 1 (Day 1, before BCG and avelumab treatment)

BCG maintenance phase:

- Day 1 of Month 3 and 6 Maintenance: before BCG and avelumab treatment

Blood specimen will be sent to the Stephenson Cancer Center biorepository for storage, which will be analyzed for immune profile changes if collaborative funding is available.

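### On-study research blood is tied to starting Month 3 or Month 6 maintenance, so the paired-blood biomarker set is enriched for responders and, if SAP 5.b is applied by specimen, baseline blood from early failures is discarded

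*SAP*

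**What the plan says.** **Objective.** Protocol 2.1.4 gives the exploratory aim: "To identify potential biomarkers that would associate with tumor response from the combination of avelumab and intravesical BCG". Protocol 7.3 adds how: "We will assess immune profile in the pre- and post- treatment urine and blood as potential biomarkers".

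**Population.** SAP section 5.b: "the biomarker population will comprise all evaluable patients who have sufficient baseline and on-study biomarker measurements". Evaluable patients (SAP 5.c) are those "who receive at least 5 doses of intravesical BCG and avelumab IV weekly during induction treatment and complete the first post-treatment cystoscopy" and/or urine cytology. Section 5.b neither names blood or urine nor defines sufficiency, and there is no separate baseline-only set. SAP section 10 rules out imputation.

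**Blood.** A baseline sample is taken on induction Day 1. The later samples are taken "at pre-dose on day 1 of month 3 and month 6 maintenance therapy" (Table 7 note g). Protocol 7.3.2 repeats this: "Day 1 of Month 3 and 6 Maintenance: before BCG and avelumab treatment". No research blood is stated for Day 22, Day 43, repeat induction or end of treatment (EOT).

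**Urine.** Table 7 note h: "Urine sample will be collected at pre-dose on days 1, 22 and 43 of induction treatment", and again on Day 1 of Month 3 and Month 6 maintenance.

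**Who reaches maintenance.** Under Protocol 6.7, progression ends study treatment. Under 6.3.2, persistent disease at the Month 3 cystoscopy without progression may lead to a repeat induction. Under 2.2.2, "Patients with persistent or recurrent high-grade disease at 6 Month cystoscopy will be taken off treatment", while low-grade recurrence does not interrupt treatment.

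**The concern.** An analysis relating a marker to response needs the marker in both responders and non-responders. For blood, the on-study draw is attached to a treatment event, the first day of a maintenance course, and starting that course depends partly on the disease assessment just before it. Whether the sample exists is then linked to the response it is meant to be related to.

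Two things are at stake. The change in blood markers would be estimated in a set that under-represents early failures, so any association would mainly describe patients who did well enough to continue. In addition, the requirement for both a baseline and an on-study measurement could exclude Day 1 blood already collected from the early failures, although a baseline comparison needs no later sample.

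**Working it through.** The documents give no sample size, power or precision figure for the biomarker analysis, so there is no plan figure to reproduce on this point. The only precision figure in the plan, the 37.6% Wilson lower bound for 60% completion in 18 patients, does reproduce (37.6% to 78.9%), but it concerns treatment completion and has no bearing here.

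**Step 1. Trace the samples by clinical course**, for patients who meet the evaluable definition.

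| Course | On-study urine | On-study blood |
|---|---|---|
| Starts Month 3 maintenance, continues | Day 22, Day 43, Months 3 and 6 | Months 3 and 6 |
| Starts Month 3 maintenance, high-grade disease at Month 6 | Day 22, Day 43, Month 3 | Month 3 only |
| Low-grade recurrence at Month 6, continues | as first row | as first row |
| Repeat induction, later starts Month 6 maintenance | Day 22, Day 43, Month 6 | Month 6 only |
| Repeat induction, never starts Month 6 maintenance | Day 22, Day 43 | none |
| Stops by Month 3 | Day 22, Day 43 | none |

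Only the last two rows have no on-study blood. Every row has on-study urine by schedule, because Days 22 and 43 precede the Month 3 cystoscopy.

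**Step 2. Show the direction of the selection (assumed rates).** The documents give no expected complete response (CR) rate. Take the planned 18 evaluable patients and assume a 3-month CR rate of 20%, 40% or 60%: 18 × 0.2 = 3.6, 18 × 0.4 = 7.2 and 18 × 0.6 = 10.8, rounded to R = 4, 7 or 11 responders, leaving N = 14, 11 or 7 non-responders. Let f be the share of non-responders with no on-study blood, and suppose all responders have theirs. The responder share in the paired-blood set is R / (R + N(1 − f)).

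| R / N | f = 0 | f = 0.25 | f = 0.5 | f = 0.75 | f = 1 |
|---|---|---|---|---|---|
| 4 / 14 | 22% | 28% | 36% | 53% | 100% |
| 7 / 11 | 39% | 46% | 56% | 72% | 100% |
| 11 / 7 | 61% | 68% | 76% | 86% | 100% |

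For example, with R = 7 and f = 0.5: 7 / (7 + 11 × 0.5) = 7 / 12.5 = 56%. At f = 1 no comparison is possible; at f = 0 nothing is lost. For urine, f is 0 by schedule.

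**Step 3. Illustrate the cost to a baseline-blood comparison.** Assume 11 responders, 7 non-responders and a two-sided 5% t test. Power comes from the noncentral t distribution with noncentrality d√(n₁n₂/(n₁+n₂)) and n₁+n₂−2 degrees of freedom.

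| Difference d (SD) | 7 kept | 6 kept | 4 kept | 2 kept |
|---|---|---|---|---|
| 0.8 | 34% | 31% | 25% | 16% |
| 1.25 | 68% | 63% | 51% | 32% |
| 1.5 | 83% | 79% | 66% | 43% |

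The effect sizes, the 11/7 split and the numbers kept are all assumptions. The plan specifies no t test for biomarkers.

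**The case against.** The strongest reply is that SAP 5.b does not require blood. Urine is a planned biomarker specimen, and every evaluable patient should have on-study urine whatever the response. If any specimen meets the requirement, non-responders stay in the biomarker population. This stands. A reader might infer that non-responders drop out of the biomarker analysis altogether; the documents do not support that. The selection concerns paired blood, and the loss of baseline blood follows only if 5.b is applied specimen by specimen, which the wording leaves open.

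A reader might also infer that the paired-blood set would be almost all responders. That is not supported either. Low-grade recurrence at Month 6 does not stop treatment. A patient who starts Month 3 maintenance and fails at Month 6 already has a Month 3 sample. Repeat induction is permitted, not mandated, and some of those patients may reach Month 6 maintenance. Some patients will stop early for toxicity, which need not be related to response.

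Nor can the power figures be read as this plan's loss. The plan's 60% is an expected completion rate for Month 6 maintenance, and its complement is not a count of non-responders. At 0.8 SD, power is only 34% with every sample kept, so the comparison is weak under any population rule.

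Finally, paired samples do suit the stated pre- and post-treatment aim, the objective is exploratory, and Protocol 7.3 makes the assays conditional on collaborative funding. All of this lowers the severity. None of it removes the link between having on-study blood and response.

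**Conclusion.** The point holds for blood only. Patients who stop by Month 3, and those who have repeat induction without ever starting Month 6 maintenance, have no scheduled on-study blood. The paired-blood set is therefore enriched for responders, provided non-responders miss the draw more often than responders do, as the continuation rules imply. Applied by specimen, SAP 5.b would also drop these patients' baseline blood from the association with response. Because neither sufficiency nor the specimen is defined, that could be decided after the data are seen.

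The amount of enrichment cannot be derived from the documents. It ranges from none to complete across the assumed values of f, and the power figures show only what losing a few patients costs in a study of about 18. Severity is minor: no primary, secondary or safety conclusion depends on it.

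**What to change.** 1. **SAP 5.b.** Define the biomarker set by specimen and time point. Analyse baseline blood and urine markers in all evaluable patients with a baseline sample and known response status, with no on-study sample required. Keep the paired set for change-from-baseline analyses only. This is a wording change and costs nothing.

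2. **Protocol 7.3.2 and Table 7 note g.** Collect the Month 3 and Month 6 research blood at the corresponding disease assessment, or at EOT if treatment stops, whether or not maintenance BCG follows. This needs a short amendment, plus one extra research tube and its handling for a few patients. It affects sampling only and leaves treatment unchanged. It has to be made prospectively, because blood not drawn at the time cannot be recovered.
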